8.3.1 Eligibility criteria

8.3.1.1 Inclusion criteria

Subjects will be enrolled if they meet all of the following criteria:

- 1. Male/Female subjects ≥6 and ≤10- year old
- 2. AsIgE ≥ class 2 (RAST) or positive prick test for at least one perennial allergen
- 3. Acute infectious rhinitis/rhinosinusitis for ≤48h before trial entry
- 4. Patient presenting with fever ≥ 37.5 °C at screening
- Symptoms of headache, muscle ache, chilliness, sore throat, blocked nose, runny nose, cough, sneezing with a total score ≤9 (according to a physician-rated symptom score; scale: 0 → 3 [0: no symptom to 3: severe intensity])
- 6. At least one of these symptoms: sore throat, runny nose or blocked nose (i.e., with a score ≥1)
- 7. Written consent obtained from parent/legal guardians
- 8. Written assent obtained from patient

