9.4 Secondary endpoints

The analysis of the secondary endpoints will involve multivariate analysis.

The selection of variables in multivariate analysis will be performed using a 0.2 significance level and a stepwise method. Whole the multivariate analyses specified below involve the treatment and, in order to adjust for confounding, all the potential confounding factors as explanatory variables.

The analysis of the impact of the treatment chosen on the primary endpoint will be enriched by means of a multivariate regression model with the AUC of the WURSS-K during first 10 days of symptoms as dependent variable.

The impact of the treatment chosen on the cold symptoms' duration will be analysed by means of a Cox model.

The impact of the treatment chosen on the risk to develop respiratory complication requiring antibiotic prescription during a 20-day follow-up period will be analyzed by a multivariate logistic model.

The impact of the treatment chosen on the intake of conventional common cold medication (antibiotics, antipyretics, mucolytics, decongestants, antitussives, systemic and topical corticosteroids) will be analyzed by multivariate Poisson regressions for the numbers of days and a multivariate logistic regression for the frequency.

The impact of the treatment chosen on the number of family members in close contact developing common cold symptoms after the patient all over the study period will be analyzed by means of a multivariate Poisson regression.

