6.3. Statistical/Analytical issues

6.3.1. Significance level

All statistical analyses will be performed at the 0.05 global significance level (type I error rate), using two-sided tests.

The statistical results are conclusive for the primary efficacy criterion.

All the other statistical results have to be considered within a descriptive perspective and not as inferential issues. No adjustment for Type I error is done. P-values of statistical tests will be provided for information only.

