10.2. Analysis of the secondary efficacy criteria

The analysis of the secondary endpoints will involve multivariate analysis.

The selection of variables in multivariate analysis will be performed using a 0.20 significance level and a stepwise method. Whole the multivariate analyses specified below involve the treatment and, in order to adjust for confounding, all the potential confounding factors as explanatory variables:

- Temperature at baseline (°C);
- Symptoms' scores at baseline.

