10.2.3. Impact of the treatment chosen on the risk to develop respiratory complication requiring antibiotics prescription

The impact of the treatment chosen on the risk to develop respiratory complication requiring antibiotic prescription during a 20-day follow-up period will be analysed by a multivariate logistic model. Subjects will be analysed on the FAS.

10.2.4. Impact of the treatment chosen on the intake of a conventional cold medication

The impact of the treatment chosen on the intake of a conventional common cold medication will be analysed on the FAS.

Common cold medications are antibiotics, antipyretics, mucolytics, decongestants, antitussives, systemic and topical corticosteroids.

The use/non-use of these medications (if the patient used it at least one day from D1 to D30, or if he/she never used it) will be modelled by a multivariate logistic regression.

The number of days of intakes of these medications is defined as follows:

- A day is counted when the patient used at least one of these medications this day;
- Each day is counted once, whatever the number of these medications used this day;
- The total number is the sum of all distinct days of use of these medications, from D1 to D30.

The number of days of intakes of these medications will be modelled by a multivariate Poisson regression.

The same analyses will be performed for each category of medications: antibiotics, antipyretics, mucolytics, decongestants, antitussives, systemic and topical corticosteroids.

10.2.5. Impact of the treatment chosen on the number of family members in close contact developing common cold symptoms

The impact of the treatment chosen on the number of family members in close contact developing common cold symptoms after the patient all over the study period will be analysed by means of a multivariate Poisson regression. Subjects will be analysed on the FAS.

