Q1/Q3	XX / XX	XX / XX
Min/Max	XX / XX	XX / XX
Hazard Ratio [95%CI]	XX.X [XX.X; XX.X]	
p-value (Wald)	XXX	

Table 14.2.2.3. Impact of the treatment chosen on the risk to develop respiratory complication requiring antibiotic prescription during a 20-day follow-up period – Full Analysis Set

	Healsea Children N=XX	Conventional therapy N=XX
Use of antibiotics during 20-day follow-up period		
N	XX	XX
Missing	XX	XX
No	XX.X (XX.X%)	XX.X (XX.X%)
Yes	XX.X (XX.X%)	XX.X (XX.X%)
Logistic model :		
Odds Ratios [95%CI]		
Treatment	XX.X [XX.X; XX.X]	
...	XX.X [XX.X; XX.X]	
p-values (Wald)		
Treatment	XXX	
...	XXX	

Table 14.2.2.4.X. Impact of the treatment chosen on the intake of XXX – Full Analysis Set

	Healsea Children N=XX	Conventional therapy N=XX
Number of days of intakes of XXX		
N	XX	XX
Missing	XX	XX
0	XX.X (XX.X%)	XX.X (XX.X%)
1	XX.X (XX.X%)	XX.X (XX.X%)
2	XX.X (XX.X%)	XX.X (XX.X%)
...	XX.X (XX.X%)	XX.X (XX.X%)
Poisson regression :		
Type 3 Tests of Fixed Effects		
Treatment	XXX	
...	XXX	
Use of XXX		
N	XX	XX
Missing	XX	XX
No	XX.X (XX.X%)	XX.X (XX.X%)
Yes	XX.X (XX.X%)	XX.X (XX.X%)
Logistic model :		
Odds Ratios [95%CI]		
Treatment	XX.X [XX.X; XX.X]	
...	XX.X [XX.X; XX.X]	
p-values (Wald)		
Treatment	XXX	
...	XXX	

Table 14.2.2.5. Impact of the treatment chosen on the number of family members in close contact developing common cold symptoms after the patient all over the study period – Full Analysis Set

	Healsea Children N=XX	Conventional therapy N=XX
Number of family members in close contact developing common cold symptoms after the patient all over the study period		
N	XX	XX
Missing	XX	XX
0	XX.X (XX.X%)	XX.X (XX.X%)
1	XX.X (XX.X%)	XX.X (XX.X%)
2	XX.X (XX.X%)	XX.X (XX.X%)
...	XX.X (XX.X%)	XX.X (XX.X%)
Poisson regression :		
Type 3 Tests of Fixed Effects		
Treatment	XXX	
...	XXX	

Table 14.2.3. Concomitant treatments – Full Analysis Set

ATC1 - ATC2	Healsea Children N=XX	Conventional therapy N=XX	Total N=XX
Subjects with at least one concomitant medication			
All	XX (XX.X%)	XX (XX.X%)	XX (XX.X%)
XXXXX			
All	XX (XX.X%)	XX (XX.X%)	XX (XX.X%)
XXXXX	XX (XX.X%)	XX (XX.X%)	XX (XX.X%)
XXXXX	XX (XX.X%)	XX (XX.X%)	XX (XX.X%)

Table 14.2.4.1.1. Summary of non-related adverse events – Full Analysis Set

	Healsea Children N=XX	Conventional therapy N=XX		Total N=XX		
	n (%)	[E]	n (%)	[E]	n (%)	[E]
Number and percentage of subjects with non-related / Number of non-related						
Adverse event	XX (XX.X%)	XXX	XX (XX.X%)	XXX	XX (XX.X%)	XXX

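### Days of cold-medication use are modelled by plain Poisson regression with no dispersion handling, so the Type 3 p-value, the only Poisson result shown, is miscalibrated whenever variance and mean differ (minor)

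*SAP*

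**What the plan says.** SAP 10.2.4 defines the outcome as a count of distinct days from D1 to D30: "A day is counted when the patient used at least one of these medications this day". Each child therefore contributes a number from 0 to 30. Of the model it says "The number of days of intakes of these medications will be modelled by a multivariate Poisson regression", and then "The same analyses will be performed for each category of medications". That gives eight day-count models, one combined and one for each of seven classes (SAP 13.1, tables 14.2.2.4.1 to 14.2.2.4.8). Protocol 9.4 agrees: medication intake "will be analyzed by multivariate Poisson regressions for the numbers of days".

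Neither document names a scale parameter, a robust variance, a negative binomial model or a dispersion check. SAP 10.2 adjusts the secondary models "in order to adjust for confounding, all the potential confounding factors as explanatory variables", and lists baseline temperature and baseline symptom scores, selected stepwise at 0.20.

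The block headed "Number of days of intakes of XXX" in mock table 14.2.2.4.X (SAP 13.2) tabulates the days and then shows only Type 3 tests from the Poisson model. The same table gives an odds ratio with 95% CI for use versus non-use.

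On status, SAP 6.3.1 treats only the primary criterion as conclusive. For the rest, "P-values of statistical tests will be provided for information only".

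**The concern.** Poisson standard errors are right only if the variance of the count equals its mean. Days of medication use are unlikely to meet that condition. Children who never take a drug contribute zeros, which the SAP expects because it models use and non-use separately. Children who take it contribute runs of consecutive days rather than independent events. If few children use a class, the variance can be several times the mean and the p-value is too small. If nearly all use it for similar periods, the variance can fall below the mean and the p-value is too large.

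What is at stake is the reading of one row in each of eight tables. The mock tables for the ANCOVA, Cox and logistic models all give an estimate with an interval. The Poisson block gives a p-value alone, so a miscalibrated p-value is the only inferential result for days of use. Protocol 8.1.4 expects the device to reduce rescue medication, and a falsely small p-value would appear to confirm this.

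**Working it through.** **Inputs from the documents.** 100 children per group (SAP 4); two-sided 0.05 level (SAP 6.3.1); outcome 0–30 days (SAP 10.2.4). The plan's only design figure is 80% power for a standardised difference of 0.4 with 100 per group. It reproduces (t-test power 80.4%; 99.1 per group needed for 80%), but it concerns the AUC. No figure is given for the medication-day models.

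**Inputs assumed.** The share of users p and mean course length m, since the documents state neither.

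**Step 1: dispersion.** If a share p of children take a fixed course of m days and the rest take none:
- mean = pm; variance = pm² − (pm)² = m²p(1−p)
- variance/mean = φ = m(1−p)

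If course length is instead 1 + Poisson(m−1), φ = [(m−1+m²)p − (pm)²]/(pm). For p = 0.1, m = 5 this is (2.9 − 0.25)/0.5 = 5.3. For p = 0.3, m = 5 it is (8.7 − 2.25)/1.5 = 4.3.

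**Step 2: actual error rate.** The Poisson standard error is off by a factor √φ, so the actual two-sided rate is about 2[1 − Φ(1.96/√φ)]. With fixed courses:
- p = 0.3, m = 3: φ = 2.1, rate 17.6%
- p = 0.1, m = 7: φ = 6.3, rate 43.5%
- p = 0.5, m = 2: φ = 1.0, rate 5%
- p = 0.7, m = 3: φ = 0.9, rate 3.9%
- p = 0.7, m = 2: φ = 0.6, rate 1.1%

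**Step 3: null simulation.** 20,000 trials per cell, no group difference, likelihood-ratio test, courses capped at 30 days. Course length is fixed, 1 + Poisson, or widely spread (1 + negative binomial, shape 2). Rejection at nominal 5%:

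| Users, mean course | Fixed | 1 + Poisson | Spread |
|---|---|---|---|
| 10%, 7 days | 42.4% | 47.1% | 53.1% |
| 30%, 5 days | 30.1% | 35.1% | 42.4% |
| 50%, 5 days | 21.9% | 27.5% | 37.8% |
| 70%, 4 days | 8.0% | 16.1% | 26.1% |
| 90%, 6 days | 1.3% | 10.5% | 29.4% |
| 90%, 3 days | 0.0% | 4.8% | 12.5% |

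Fixed short courses confirm Step 2: 3.9% (70%, 3 days), 1.2% (70%, 2 days), 5.5% (50%, 2 days).

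**Step 4: does covariate adjustment help?** Two baseline covariates that predict use (log-odds 0.4 per SD) were added, with 1 + Poisson courses of mean 5 days. The likelihood-ratio test still rejected 38.7% (10% users), 33.1% (30%), 27.4% (50%) and 6.2% (95%). Both covariates were forced in, so this approximates the planned stepwise model rather than reproducing it.

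**Step 5: robust variance.** With 1 + Poisson 5-day courses, a sandwich variance gave 4.3% (10% users), 4.9% (30%), 5.1% (50%), 4.8% (70%), 5.3% (95%) and 5.0% (100%). With more variable courses it gave 5.2–6.3% for 10% or more users.

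**Step 6: groups without users.** The chance that at least one group has no user is 1 − [1 − (1−p)^100]². This is about 1.2% at p = 0.05 and 25% at p = 0.02. The rate ratio then cannot be estimated.

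**The case against.** The strongest objection concerns consequence. SAP 6.3.1 makes these results descriptive, and the table also shows the distribution of days and a logistic odds ratio that dispersion does not touch. Families choose their own group (Protocol 8.2), so even a well-calibrated Poisson p-value would not isolate a device effect. All of this stands, and it is why the point is minor. It does not make the p-value correct: a figure given for information should still mean what it says.

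The second objection concerns direction. A reader might infer that the p-value is too small for every class that only some children use. The documents do not support that. At 50–70% users with short, uniform courses the plain test is correct or conservative. Inflation is consistent across all three course types only at low use with courses of three days or more.

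Two further inferences also go too far. The entry criterion "Patient presenting with fever" might suggest that nearly every child takes an antipyretic, which would exempt that class and the combined count. No passage states antipyretic use, and near-universal use can itself give inflation when durations vary. Nor do the results support dropping p-values below some share of users. At 5% users the robust test rejected 3.5–4.8% with 1 + Poisson courses and 7.0–7.5% with more variable ones, and the documents contain no such cutoff.

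**Conclusion.** The omission is real and its consequence is limited. Poisson regression with no dispersion handling gives a miscalibrated Type 3 p-value whenever the variance of medication days differs from the mean.

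Under assumed use rates and course lengths, with 100 per group and a nominal 5%:
- 10–30% users, 3–7-day courses: about 17–53% rejection, from fixed to widely spread courses.
- 50–70% users, 2–5-day courses: from about 1% (fixed 2-day courses, 70% users) to about 37–38% (spread 5-day courses, 50% users).
- Near-universal use: conservative, correct or inflated, depending on the spread of durations.

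Which range applies to a given class cannot be settled from the documents. A reader might conclude that the medication-day estimates or the trial's main result are unsound. They are not: overdispersion does not bias the rate ratio, and the primary AUC analysis and the logistic analysis of use are unaffected. Severity: minor.

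**What to change.** In SAP 10.2.4, specify a robust (sandwich) variance for all eight medication-day Poisson models. It is approximately right in either direction (about 4–6% for 10% or more users), so nobody has to predict the dispersion of each class. Add the rate ratio with 95% CI to mock table 14.2.2.4.X. State that where one group has no users, the rate ratio cannot be estimated and users and days are reported descriptively.

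The cost is a few lines of SAP text, one variance option per model and one added row in the shared mock table. No new data are needed. The downside is wider intervals for most classes than plain Poisson would give.

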10.3. Concomitant treatments

Concomitant treatments are coded using the WHO-DRUG dictionary version 2021 Q1.

All treatments taken at least once after reference first date or appeared during the study will be summarised by Anatomical Therapeutic Class (ATC) and substance name. The number and percentage of subjects in each category will be computed.

Subjects will be counted only once within these ATC categories. They will be analysed on the FAS.

Note: a medication which began before the reference start date and which is ongoing after the reference start date is counted in “previous medications” (see §8.2) and not in “concomitant medications”.

10.4. Non-related adverse events

In the following paragraph, for a smoother reading:

- adverse events will be referred as AE;
- treatment-emergent adverse events will be referred as TEAE.

Adverse events are coded using the MedDRA dictionary version 20.1. They are classified by System Organ Class and Preferred Term.

For efficacy analyses, only non-related AEs are considered, i.e. adverse events with a relationship to study device equal to “not related”. These analyses will be performed on the FAS.

An adverse event will be considered as a treatment-emergent adverse event (TEAE) if:

- it was reported at least one day after screening, or at least two days after screening in the case of the AE “rhinitis”;
- it was not present prior to the reference start date;
- it was present prior to the reference start date and worsened during the study (increase of intensity);
- it reappears after the reference start date (finished before the reference start date).

Missing or incomplete dates will be estimated as described in §6.4.4 in order to determine the TEAEs, but they will be presented as reported in CRF in the data listings. Generally, an adverse event for which the onset date is missing or incomplete and does not permit to identify the onset according to the date of the reference start date (i.e. missing onset day and month/year corresponding to the reference start date) will be considered as treatment-emergent.

Note: if the intensity/severity is missing, a conservative approach will be adopted and the intensity/severity will be considered as severe.

A given treatment-emergent adverse event (according to the MedDRA terminology) will be counted only once per subject. If a subject experienced several AEs in the same SOC/PT, the most severe intensity will be retained for this SOC/PT.

- Summary of non-related adverse events

A summary table will be produced:

- number and percentage of subjects with at least one non-related adverse event (AE);
- number and percentage of subjects with at least one non-related AE leading to definitive study device discontinuation;
- number and percentage of subjects with at least one non-related TEAE.

The number of non-related AEs of each category will also be provided in this table.

- Analysis of non-related treatment-emergent adverse event

The number and percentage of subjects with non-related TEAEs will be summarised by System Organ Class and Preferred term.

The number of non-related TEAEs of each category will also be provided in this table.

All non-related AEs leading to definitive discontinuation of the trial device will be listed if applicable.

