- **Safety:** All adverse events and incidents will be listed, but only treatmentemergent adverse events/incidents (non-serious + serious)/ undesirable expected side effects will be summarized.

Two groups (called treatment groups) will be extracted from the cohort according to the treatment chosen by the patient.

Adverse events and incidents will be summarized by the number and percentage of patients (by treatment group), classified by System Organ Class and Preferred Term as defined by MedDRA dictionary.

For a given treatment group, a given adverse event will be counted treatment emergent only once per patient during the treatment period.

Frequency and percentage of patients with at least one reported adverse event/ incident/ expected side effect will be tabulated by System Organ Class and by treatment group.

Version: **2.0**; **08** Sep **2021** Page **19** of **61** Study Number: **LPH-2101**

3. Flow Chart

	ACUTE PHASE			FOLLOW-UP			
Visit name	Screening/Inclusion	At home	Telephone call	End of treatment	At home	Telephone call	End of study
Visit Number	V1		TC1	V2		TC2	V3
Days/Weeks	D1	D1 – D10	D5±2	D10±2	D11 – D30±5	D20±2	D30 ± 5
Screening and General Assessments							
Information and consent process	Х						
Eligibility criteria	Х						
Demography and Medical history	Х						
Physical and clinical examination	X			Х			Х
Ongoing medication	Х						
Patient's choice for using Healsea® Children self-administration or not	Х						
Treatment							
Acute phase (Healsea® Children or no saline irrigation as add on therapy)		Х					
Assessments							
Subject e-diary (WURSS-K)		Х			X*		
Adverse Events/incidents/undesirable expected side effects and concomitant medication reporting	Х	Х	Х	Х	х	х	Х

^{*} After D10, the WURSS-K will be assessed once daily until the subject feels not sick for two consecutive days if applicable.

Version: **2.0; 08 Sep 2021** Study Number: **LPH-2101**

4. Identification and description of the investigational Device

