 incidents/expected undesirable side effects, concomitant medications, and contamination of
 relatives in the e-diary. The legal guardians will access the e-diary website
 (https://me.vieodoc.net) using a smartphone and logging in with a randomly assigned
 username and Pin code. Data recorded in the e-diary will be at the same time uploaded in the
 e-CRF.

D1-D10 (at home):

The patients will be asked to complete the electronic diary daily (WURSS-K assessed once daily in the evening, taking in account the symptoms from the morning to the evening, adverse events/incidents/expected undesirable side effects and concomitant medications, contamination of relatives) and to report Healsea® Children intake if applicable. For the Healsea® Children treated-group, compliance will be indirectly assessed by the question: "do you use the nasal spray as

Version: **2.0**; **08** Sep **2021** Page **35** of **61** Study Number: **LPH-2101**

recommended (1 puff 2 sec in each nostril twice a day)?". If necessary, the parent(s) will help their child in this task.

D5 (Day 5±2, at home): Telephone call 1

The Investigator or his/her delegated designee will call the patient to review patient status and study progress, adverse event/incidents/expected undesirable side effects and concomitant treatments.

Visit 2 (V2) - (Day 10±2): end of treatment

The investigator or his/her delegated designee will:

- Perform a physical and clinical examination,
- Record the common cold symptoms if they persist,
- Validate the adverse events/incidents/expected undesirable side effects and concomitant medications reported in the e-CRF through the e-diary and report any new relevant safety event.

For patients receiving Healsea® children, the treatment will be stopped at D10. The patients for whom common cold symptoms persist, will be instructed to continue to score the WURSS-K until the subject feels not sick for two consecutive days.

D11-D30 (at home):

After D10, the WURSS-K will be assessed once daily until the subject feels not sick for two consecutive days if applicable. The patients will be asked to complete the electronic diary daily (WURSS-K if applicable, adverse events, concomitant medications, and contamination of relatives). If necessary, the parent(s) will help their child in this task.

D20 (Day 20±2, at home): Telephone call 2

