9.5 Safety

All adverse events/incidents/expected side effects will be listed, but only treatment-emergent adverse events/incidents (non-serious + serious) will be summarized.

Two groups (called treatment groups) will be extracted from the cohort according to the treatment chosen by the patient.

Page **39** of **61** Version: 2.0; 08 Sep 2021

Adverse events/incidents/expected side effects will be summarized by the number and percentage of patients (by treatment group), classified by System Organ Class and Preferred Term as defined by MedDRA dictionary.

For a given treatment group, a given adverse event will be counted treatment emergent only once per patient during the treatment period.

Frequency and percentage of patients with at least one reported adverse event/incident / expected side effects will be tabulated by System Organ Class and by treatment group.

10. Data management

Subject data will be entered into an electronic case report form.

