3. STUDY DESIGN

This is a prospective, open label, interventional, national (Poland), multicentric study. During this prospective interventional study, one cohort of IgE-dependent allergic children with early symptoms of infectious rhinitis will be followed, children being treated with Healsea® Children on top of common cold conventional therapies or with conventional therapies only (nasal irrigation excepted). This study aimed to confirm the benefit of Healsea® Children in a real life setting in children with perennial allergy.

Investigational plan description (see Figure 1):

- **Visit 1 (V1) – (Day 1): Screening/Inclusion**

Information and provision of the information sheet to legal guardians and participants, consent and assent signatures, demographic data and medical history, ongoing medication, physical and clinical examination, inclusion/non-inclusion criteria, record of patient choice regarding Healsea® Children use.

- **D1-D10 (at home):**

Daily completion of the electronic diary (WURSS-K, adverse events/incident/ undesirable expected side effects and concomitant medications, contamination of relatives if applicable, Healsea® Children daily administration if applicable).

– **D5±2 (at home): Telephone call 1**

Investigator/nurse call to review patient status and study progress, adverse event/incident/undesirable expected side effects and concomitant treatments.

– **Visit 2 (V2) – (Day 10±2): End of treatment**

End of Healsea® Children nasal spray treatment if applicable, assessment of symptoms, diary review, reporting of adverse events/incident/undesirable expected side effects.

– **D11-D30±5 (at home):**

Daily completion of the diary (Adverse event, concomitant medications, contamination of relatives if applicable, WURSS-K if applicable, until the subject feels not sick for two consecutive days).

– **D20±2 (at home): Telephone call 2**

Investigator/nurse call to review patient status and study progress, adverse events and concomitant treatments.

– **Visit 3 (V3) – (Day 30±5): End of study**

Physical and clinical examination, diary review, reporting of adverse events and concomitant treatments

The maximal study duration for each subject is 35 days.

Visit name	ACUTE PHASE				FOLLOW-UP		
	Screening/Inclusion	At home	Telephone call	End of treatment	At home	Telephone call	End of study
Visit Number	V1		TC1	V2		TC2	V3
Days/Weeks	D1	D1 – D10	D5±2	D10±2	D11 – D30±5	D20±2	D30 ± 5
Screening and General Assessments							

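### SAP 10.4 gives treatment-emergent non-related adverse events a start but no end, so onsets on D11–D35, after the spray has stopped, are counted

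*SAP*

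**What the plan says.** SAP 10.4 applies to adverse events rated not related to the device. It lists four criteria for treatment-emergence:

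- reporting at least one day after screening (two days for rhinitis);
- "it was not present prior to the reference start date";
- worsening of an earlier event, worded as "it was present prior to the reference start date and worsened during the study (increase of intensity";
- reappearance after the reference start date.

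The counting rule follows: "A given treatment-emergent adverse event (according to the MedDRA terminology) will be counted only once per subject". None of this names a last day. SAP 6.4.1 sets the reference start date at the inclusion visit and the reference end date at the end of the subject's participation, not at the end of treatment.

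Protocol 9.5 has almost the same counting sentence with a time limit: "a given adverse event will be counted treatment emergent only once per patient during the treatment period". The synopsis repeats it. On the length of treatment, protocol 8.3.11 says "For patients receiving Healsea® children, the treatment will be stopped at D10". On follow-up, SAP 3 has adverse events recorded in the diary to D30±5 and adds "The maximal study duration for each subject is 35 days".

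SAP 12, which lists changes from the planned analysis, mentions only the definition of symptom duration. Related events are handled in SAP 11.2, which states no treatment-emergent filter and no time window.

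**The concern.** The label says treatment-emergent, but a gastroenteritis starting on D28, 18 days after the last planned spray, would earn it. Most of the window is then time when neither group uses the device, and ordinary seasonal illness in both groups is added to whatever happened on treatment.

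Two features of the SAP make this more than wording. First, Table 14.2.4.1.1 has one row for any non-related event and another for treatment-emergent ones. Events are collected only from the inclusion visit onward, so without an end date the second row nearly repeats the first. Second, no planned table separates D1–D10 from later days, so the tables never show the on-treatment comparison. Causality is also judged open label. A device effect that nobody recognises as such would be rated not related and would land in exactly these tables.

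**Working it through.** The plan attaches no figure to this rule and gives no adverse event rate. Its only sample-size figure concerns the AUC: 100 per group for a standardised difference of 0.4 at 80% power. That reproduces (99 per group needed; 80.7% power at 100) and is not affected.

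**Inputs from the documents.** The window opens on D2, one day after screening (SAP 10.4). The spray stops at D10 (protocol 8.3.11). V3 falls on D30±5, so the end is D25, D30 or D35 (SAP 3).

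**Assumptions.** The daily background rate is constant and equal in both groups. In the spray group it is doubled on D2–D10 only. Where a level is needed, the background is 0.5% per day.

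1. *Off-device share of the window*, (end − 10)/(end − 1):
   - D25: 15/24 = 63%
   - D30: 20/29 = 69%
   - D35: 25/34 = 74%

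2. *Event-rate ratio shown when the true on-treatment ratio is 2*, (2 × 9 + end − 10)/(end − 1):
   - D25: 33/24 = 1.38
   - D30: 38/29 = 1.31
   - D35: 43/34 = 1.26

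3. *Patients with at least one event*, 1 − exp(−cumulative rate):
   - D2–D10: spray 1 − exp(−0.090) = 8.6%; conventional 1 − exp(−0.045) = 4.4%. The difference is 4.2 points and the ratio 1.96.
   - D2–D30: spray 1 − exp(−0.190) = 17.3%; conventional 1 − exp(−0.145) = 13.5%. The difference is 3.8 points and the ratio 1.28.

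4. *Expected events per 100 patients:*
   - D2–D10: 9.0 vs 4.5, a difference of 4.5.
   - D2–D30: 19.0 vs 14.5, again a difference of 4.5.
   - Treating counts as Poisson, the standard deviation of the difference rises from √13.5 = 3.7 to √33.5 = 5.8.

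5. *Sensitivity to the background level.* Over follow-up to D30, the patient-level difference is multiplied by the probability of no background event on D11–D30. Take a conventional-group risk of 2%, 10% or 20% over D1–D10, doubled with the spray. The difference then goes from 2.0 to 1.9 points (× 0.98²), from 10.0 to 8.1 (× 0.90²) or from 20.0 to 12.8 (× 0.80²). The risk ratio shows as 1.33 to 1.26 instead of 2.0 across that range.

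**The case against.** The strongest reply is about reach. A reader might infer that the safety analysis of the device is diluted, so that any excess on treatment is harder to see. The documents do not support that. The rule in SAP 10.4 stands in the efficacy chapter and covers only events rated not related. Related events go to SAP 11.2, whose text has no treatment-emergent filter. The listed title of Table 14.3.1.2 does say treatment-emergent, but the corresponding mock table (numbered 14.3.1.4) says incidents. That is a labelling mismatch. It does not show that off-device illness fills the table.

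A reader might also infer that protocol 9.5 formally defines treatment-emergence as ending at D10. It does not: the phrase sits in a once-per-patient counting sentence, and the protocol's safety objective and endpoint cover the whole study. Complications in the 20-day follow-up are also an objective, so later events belong somewhere in the report.

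Thirdly, the mock tables show numbers, percentages and event counts, with no ratio or test, and SAP 6.3.1 makes everything beyond the primary criterion descriptive. Onset dates are in Listing 16.2.7.1, so a determined reader could split the periods by hand.

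All of this limits the consequence, and it stands. It does not remove the open-ended window, the undeclared difference from the protocol's only time limit on the count, or the absence of an on-treatment comparison in any table.

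**Conclusion.** The point holds for the tables of non-related events (14.2.4.1.1 and 14.2.4.1.2). The SAP's treatment-emergent window has no end, the protocol's counting rule confines the count to the treatment period, and SAP 12 is silent. That much rests on the text alone, as does the off-device share of 63% to 74%.

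The dilution rests on assumed rates. With similar rates in both groups after D10, a ratio of 2.0 would appear as about 1.3. The patient-level difference shrinks little at a low background (4.2 to 3.8 points at 0.5% per day) and more at a high one. The expected difference in event counts does not shrink; it only becomes noisier. No confirmatory result is touched. The change is worth making because it is nearly free and restores agreement between the two documents.

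**What to change.** - In SAP 10.4, limit the treatment-emergent label to onset or worsening from inclusion to D10, using the same days in both groups, to agree with protocol 9.5. Alternatively, keep the whole-study window and declare the change in SAP 12.
- In either case, give Tables 14.2.4.1.1 and 14.2.4.1.2 separate row blocks for D1–D10 and D11–end of study, plus the whole-study total, so that the objective covering the full study period is still met.
- Do the same for the incident tables. State in SAP 11.2 whether a treatment-emergent filter applies, and reconcile the title of Table 14.3.1.2 with that text and with its mock table.

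The cost is a few sentences in the SAP, one period flag derived from onset dates already collected, and slightly longer tables.
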